14 SAFETY ANALYSES

The safety summaries will be presented based on the Safety Analysis Set using actual treatment. Safety variables include adverse events (AEs), clinical laboratory variables, vital signs, physical examinations, electrocardiogram (ECG) and Global Clinician Assessment of Suicidality (GCAS) variables. Safety variables will be summarized by treatment group using descriptive statistics.

14.1 Adverse Events

All adverse events will be coded using the MedDRA Version 19.0 or newer.

An AE (classified by preferred term) will be considered a treatment-emergent AE (TEAE) if started after first study dose administration and no later than last study dose date + 30. AEs reported on Day 1 based on Baseline (pre-dose) findings (e.g. clinically significantly abnormal vital signs, laboratory test results, or electrocardiogram parameters) will not be considered as TEAEs.

The event counts and the number and percentage of subjects reporting TEAEs in each treatment group will be tabulated by SOC and preferred term; and, by SOC, preferred term,

and maximum severity. If more than 1 AE occurs with the same preferred term for the same subject, then the subject will be counted only once for that preferred term using the most severe occurrence for the summarization by severity. In addition, the event counts and the number and percentage of subjects with TEAEs classified by the Investigators as related to the study drug, with most frequently reported TEAEs (preferred terms reported by $\geq 5\%$ of subjects in any treatment group), with treatment-emergent serious AEs (TESAEs), with fatal AEs (i.e. events that cause death), and with TEAEs leading to discontinuation of study drug will be summarized by SOC and preferred term within each treatment group. These tables will be sorted alphabetically by SOC and then by descending subject frequency for the preferred terms (combined counts from all treatment groups) within each SOC.

The event counts and the number and percentage of subjects with any TEAEs will also be tabulated by preferred term without SOCs within each treatment group. This table will be sorted by descending subject frequency using combined counts from all treatment groups.

In addition, for the SAEs and death, the following estimated odds ratios and their 95% confidence intervals will be calculated using an exact logistic regression model with a single fixed effect for treatment group:

- Both active arms combined versus placebo;
- Pimavanserin 20 mg versus placebo;
- Pimavanserin 34 mg versus placebo.

An AE listing by subject will display all events, including those which are not treatment-emergent, and will include the verbatim term in addition to the MedDRA SOC and preferred term. This listing will also include all relevant eCRF data associated with the event: e.g. date of onset, date resolved, date of first dose, date of last dose, severity, frequency, outcome, relationship to study drug, action taken with study drug, and required therapy. When a date is presented, the study day associated with the date will also be displayed. Separate listings will be presented for subjects with SAEs, subjects with AEs leading to discontinuation and subjects who died (if any). In these listings, an indicator for treatment-emergent events will also be included.

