### Follow-up of Study Completers

Subjects who successfully complete the 12-week treatment period can enroll in an open-label safety extension study if they qualify. For subjects who discontinue prematurely from the study or who do not enroll in the open-label extension study, a follow-up safety assessment will be conducted by telephone call approximately 30 days after the last dose of study drug.

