#### **4.2      Subject Withdrawal**

In accordance with the Declaration of Helsinki and other applicable regulations, a subject has the right to withdraw from the study at any time, and for any reason, without prejudice to his or her future medical care.

If consent has been given by a legally authorized representative because the subject is not competent to provide informed consent, the authorized representative has the right to withdraw the subject from the study at any time, and for any reason, without prejudice to the subject's future medical care or any penalty or loss of benefits to the legally authorized representative.

The study partner/caregiver has the right to withdraw his or her agreement to participate in the study at any time, and for any reason, without prejudice to the subject's future medical care or any penalty or loss of benefits to the caregiver. If the study partner/caregiver withdraws agreement to participate the subject must be discontinued unless another suitable caregiver is available to sign the agreement to participate.

Subjects may be discontinued or withdrawn from the study for a number of reasons, including but not limited to those listed below:

- AEs(s) (serious or non-serious)
- The Investigator becomes aware of an impending and unexpected change in the subject's living situation (e.g., change in caregiver, change in facility, moving from home to facility, moving from one family member or caregiver's home to another) that s/he judges may cause a major disruption in the subject's behavior
- The Investigator determines that continuation in the study would be detrimental to a subject's well-being
- At the discretion of the Sponsor
- Subject fails to comply with protocol requirements
- Voluntary withdrawal of consent by subject or subject's legally authorized representative (wherever possible, the reason for withdrawal of consent should be collected)
- Subject is lost to follow-up
- Female subject becomes pregnant

Every effort should be made to complete the EOS/ET visit should a subject discontinue prematurely from the study.

If a subject is lost to follow-up, every effort should be made to phone the subject's study partner/caregiver approximately 30 days after last known contact with the subject in order to assess the subject's current status. All phone contact with the study partner/caregiver should be documented.

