For subjects who continue to be followed for safety, SAEs should continue to be reported as described in [Section 7.6.1](#).

If a subject is discontinued from the study because of an AE, every reasonable attempt should be made to follow the subject until the AE resolves or until the Investigator, in conjunction with ACADIA, deems the AE to be chronic or stable.

All SAEs will continue to be followed until the Week 12 (EOS/ET) visit, or until the Week 16 Safety follow-up visit for those subjects who do not enter the safety extension study, or until such events have resolved or the Investigator, in conjunction with ACADIA, deems them to be chronic or stable.

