## **7 ADVERSE EVENTS/SERIOUS ADVERSE EVENTS AND REPORTING**

### **7.1 Adverse Events**

Adverse events will be recorded from the time informed consent is obtained. For subjects who enroll in the open-label extension study, AEs from this study will be recorded through the completion of procedures at the Week 12 (EOS/ET) visit. Any AE occurring thereafter will be recorded in the open-label extension study. For subjects who complete the study or prematurely discontinue from the study and do not enter the open-label study, AEs will be recorded through the follow-up safety assessment (conducted by telephone call) approximately 30 days after the last dose of study drug. All AEs must be either resolved or stable at Week 12 (EOS/ET). If ongoing at the end of the study, the subject should be referred for appropriate treatment.

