### **9.8.1 Adverse Events**

All AEs will be coded using the MedDRA coding dictionary. All AEs will be listed and TEAEs will be summarized by system organ class and preferred term. A TEAE is defined as an AE that started after the first dose of study drug. Summaries by maximum severity and by relationship will also be provided. Serious TEAEs, fatal TEAEs, and TEAEs leading to discontinuation will also be summarized.

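### How long adverse events are collected depends on extension entry and early discontinuation, and the between-arm TEAE, SAE and death summaries in SAP 14.1 make no allowance for it

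*SAP*

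**What the plan says.** SAP 14.1 sets one window for every subject: an event is treatment-emergent "if started after first study dose administration and no later than last study dose date + 30". Protocol 9.8.1 gives no upper limit: "A TEAE is defined as an AE that started after the first dose of study drug". SAP 19 nevertheless declares no changes from the protocol.

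Collection is governed by Protocol 7.1 and differs between subjects:

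- Extension entrants: "AEs from this study will be recorded through the completion of procedures at the Week 12 (EOS/ET) visit", and then "Any AE occurring thereafter will be recorded in the open-label extension study".
- Completers who do not enter, and early discontinuers: "AEs will be recorded through the follow-up safety assessment (conducted by telephone call) approximately 30 days after the last dose of study drug".

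Protocol 4.2 follows the same split for SAEs, which are followed to Week 12 "or until the Week 16 Safety follow-up visit for those subjects who do not enter the safety extension study". Entry is settled after randomization: "Subjects who successfully complete the 12-week treatment period can enroll in an open-label safety extension study if they qualify" (Protocol 3.1, Follow-up of Study Completers).

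SAP 14.1 reports TEAE counts and percentages by arm. It also gives odds ratios with 95% intervals for SAEs and death, for each dose and for both doses combined against placebo. The exact logistic model has treatment group as its only term. The section speaks there of SAEs and death, although it uses the term for treatment-emergent SAEs a few lines before. Which set enters the model is not stated.

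**The concern.** The analysis window and the collection period do not match. For an entrant, the part of the window after the Week 12 visit is empty because this study does not record it, whether or not anything happened. For a non-entering completer the same part is observed. Nothing in the SAP says how the unobserved part is handled, and neither the percentages nor the odds ratios take observed time into account.

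Entry and early discontinuation can both depend on tolerability and response. If either differs by arm, the arms are observed for different lengths of time. The post-treatment time also differs in kind: it is off study drug, and the concomitant-medication restrictions of Protocol 5.7.2 end at the Week 12 (EOS/ET) visit. The SAE and death odds ratios are the only between-arm safety estimates with intervals in SAP 14, and those intervals do not cover this source of error.

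**Working it through.** **Inputs from the documents.** Week 12 visit on Day 85, follow-up call at about Day 115 with a +7-day window (SAP Table 1; Protocol Appendix A, footnote a); 111 subjects randomized 1:1:1, so 111/3 = 37 per arm. **Assumed, because the documents give no figures:** extension-entry shares, discontinuation rates, an SAE risk of 5–15% by Day 85, and a constant hazard equal in all arms.

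**1. The plan's own figure.** 85 + 30 = 115, which agrees with the stated day of the call.

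**2. Collection time per subject.**
- Entrant: to about Day 85.
- Completer who does not enter: to about Day 115, a ratio of 115/85 = 1.35.
- Early discontinuer: to last dose + 30. A last dose on Day 28 gives Day 58, and on Day 56 gives Day 86. The break-even with an entrant is 85 − 30 = Day 55.

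**3. Shift in the odds ratio if everyone completes.** With p the risk by Day 85 and f the entry share, the arm's risk is f·p + (1 − f)·[1 − (1 − p)^(115/85)]. For p = 0.10 the bracket is 0.1329. At f = 0.8 the risk is 0.8 × 0.10 + 0.2 × 0.1329 = 0.1066; at f = 0.6 it is 0.1131. The null odds ratio is (0.1066/0.8934)/(0.1131/0.8869) = 0.935. For p from 5% to 15%:

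| Entry, active vs placebo | Null odds ratio |
|---|---|
| 80% vs 80% | 1.00 |
| 80% vs 70% | 0.97 |
| 80% vs 60% | 0.93–0.94 |
| 90% vs 50% | 0.87–0.88 |
| 100% vs 0% (extreme) | 0.72–0.73 |
| 60% vs 80% | 1.07 |

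**4. Sampling error.** The approximate 95% limits divide and multiply the odds ratio by exp(1.96·√{2[1/(37p) + 1/(37(1 − p))]}). This is 8.1 at p = 5%, 4.6 at 10% and 3.6 at 15%.

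**5. Direction once some subjects discontinue.** Take arm A with 80% entrants and 20% non-entering completers: 0.8 × 85 + 0.2 × 115 = 91 days. Take arm B with 60% entrants, 20% non-entering completers and 20% with a last dose on Day 28: 0.6 × 85 + 0.2 × 115 + 0.2 × 58 = 85.6 days. Arm B has fewer entrants and is observed for less time.

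**6. What a cut at the last dose does.** Taking Day 85 as the last dose of a completer, on-treatment time is 85 days in arm A and 0.8 × 85 + 0.2 × 28 = 73.6 in arm B. The shortfall in B is 1 − 73.6/85 = 13%, against 1 − 85.6/91 = 6% under the current rules. The cut removes the gap between entrants and non-entrants but not the one from early discontinuation. Dividing events by subject-days deals with the remainder, under a roughly constant hazard.

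**7. The two TEAE definitions.** A call at the end of its window, about Day 122, is 37 days after a last dose on Day 85. An event starting 31 to 37 days after the last dose can therefore be collected and be a TEAE under Protocol 9.8.1, but not under SAP 14.1. This needs no assumption about entry rates.

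**The case against.** The strongest reply is that little turns on this. Safety is summarized descriptively, no hypothesis test is planned, and the shifts in step 3 are far inside the uncertainty in step 4. The SAP already plans disposition by arm (Section 6), exposure by arm with Kaplan-Meier curves (Section 10.1), and listings of all events, treatment-emergent or not, with onset and dosing dates (Section 14.1). In 111 subjects, individual SAEs can be read from those listings. The 30-day limit matches the protocol's collection period, and Protocol 9 leaves statistical detail to the SAP. All of this stands and keeps the point modest. It does not supply observed time by arm beside the comparisons, and SAP 19 still needs its entry.

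Some stronger readings are tempting but unsupported:

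- **That the odds ratios use the last-dose + 30 window.** SAP 14.1 does not say so. If all SAEs are counted, the collection rules set the end point and unequal observation remains, but the loss of events after day 30 would then concern the treatment-emergent tables only.
- **That the arm with fewer entrants is watched longer.** This holds if all subjects complete; step 5 shows that it can reverse.
- **That entry is simply the subject's choice.** It also requires completing 12 weeks and qualifying.
- **That calls to subjects lost to follow-up add a further block of late events.** Those calls are made "approximately 30 days after last known contact with the subject in order to assess the subject's current status", which is not a stated rule for collecting AEs.

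**Conclusion.** The mismatch is real. Collection time depends on post-randomization events, the SAP's window cannot be filled for extension entrants from this study's data, and the between-arm summaries do not account for it. Distortion arises only if entry or discontinuation differs by arm, and its direction cannot be predicted. Its size is about 0.87–0.97 on the null odds ratio for entry differences of 10 to 40 percentage points with higher entry on active drug, and about 1.07 in the reversed case tried (60% vs 80%). These figures rest on assumed entry and SAE rates, a constant hazard and full completion. A reader might infer that the planned odds ratios are unusable; with limits that span a factor of 3.6 to 8.1 either way, the documents do not support that. The unrecorded change of TEAE definition is certain but minor. Overall this is a cheap improvement to the SAP and does not undermine the safety analysis.

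**What to change.** Keep the planned tables and make these additions:

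1. In SAP 14.1, state which SAEs and deaths enter the odds ratios: all those collected, or only treatment-emergent ones.
2. Add a supportive version of the TEAE summary and of the SAE and death odds ratios, limited to events with onset through the last dose, a period that is collected for every subject. Show subject-days at risk and exposure-adjusted incidence by arm beside it, because the last-dose cut alone does not equalise observation when subjects stop early.
3. Tabulate events after the last dose separately for subjects who did not enter the extension, including those collected after day 30.
4. Record in SAP 19 that the 30-day upper limit differs from Protocol 9.8.1.

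The cost is SAP wording and one further set of tables from data already collected. The downside is that the supportive version has fewer events and leaves out SAEs and deaths after dosing stops, so it supplements the planned analysis and does not replace it.

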### **7.11 Safety Monitoring Committee (SMC)**

A Safety Monitoring Committee (SMC) will review safety and clinical outcome data, including AE and SAE data at regular intervals throughout the study. The SMC will be independent of the Sponsor and the Investigators, and will be empowered to recommend stopping or modifying the study due to safety concerns, but not for efficacy or futility.

The SMC may review blinded, unblinded, and partially unblinded data, but the Sponsor and the Investigators will remain blinded to the data provided to the SMC until the official unblinding of the clinical database at the end of the study.

In addition to their regular reviews of safety and clinical outcome data, the SMC will review formal comparisons of the rates of SAEs including deaths between the treatment groups.

The membership of the SMC will consist of clinical and statistical experts, and its mandate will be described in the SMC charter. Full details concerning the statistical methodology, as well as the frequency of interim safety analyses, will also be described in the SMC charter.

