3.3 Randomization

On Day 1 of the treatment phase, eligible subjects who meet all inclusion and none of the exclusion criteria will receive pimavanserin 34 mg per day, pimavanserin 20 mg per day or daily placebo according to a computer-generated randomization schedule. Subjects will be randomized in a 1:1:1 ratio to 1 of 3 treatment groups (pimavanserin 34 mg, pimavanserin 20 mg, or placebo), and stratified according to geographic region (North America, Europe, or Rest of World).

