3.5 Determination of Sample Size

The original planned sample size was approximately 432. For business reasons, not related to safety, the enrollment (randomization) of new subjects into the study was stopped after 111 subjects were randomized. The last subject was randomized into the study on November 2, 2017. Thus, this study is not powered to definitively evaluate efficacy measures and only descriptive summaries will be provided.

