4 ANALYSIS SETS

Randomized Analysis Set

The Randomized Analysis Set will consist of all subjects who were randomized.

Subjects will be classified according to the randomized treatment assignment.

Safety Analysis Set

The Safety Analysis Set will consist of a subset of subjects in the Randomized Analysis Set who received at least one dose of study drug.

Subjects will be classified according to the actual treatment received.

Full Analysis Set

The Full Analysis Set will consist of a subset of subjects in the Safety Analysis Set who have both a Baseline value and at least 1 post-Baseline value for the CMAI total score.

Subjects will be classified according to the randomized treatment assignment.

Per-protocol Analysis Set

The Per-protocol Analysis Set will consist of a subset of subjects in the Full Analysis Set who do not have any protocol deviation which is considered to have substantial impact on the primary efficacy outcome, change from Baseline to Week 12 in the CMAI total score. The precise reasons for excluding subjects from the Per-protocol Analysis Set will be fully defined and documented *a priori* before the clinical database lock.

Subjects will be classified according to the randomized treatment assignment.

Pharmacokinetics Analysis Set

The Pharmacokinetics Analysis Set will consist of subjects with at least one measurable pimavanserin plasma concentration.

Subjects will be classified according to the actual treatment received.

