5.1 General Data Reporting Conventions

For continuous variables, the following summary statistics will be provided: number of subjects, mean, standard error of the mean (SE), standard deviation (SD), minimum, maximum and median. Unless specified otherwise, means, medians, and confidence intervals (CIs) will be presented to one more decimal place than the raw data, and the standard deviations and standard errors will be presented to 2 more decimal places than the raw data. Unless specified otherwise, all confidence intervals will be 2-sided 95% confidence intervals.

For categorical variables, summaries will include the number and percentage of subjects in each category, using the number of subjects with non-missing values as the denominator for the percentages (unless otherwise specified). Categories with zero counts will not have zero percentages displayed. Percentages will be presented with 1 decimal place.

When converting number of days to months, it will be calculated by dividing the number of days by 365.25 and then multiplying by 12. When converting number of days to years, the number of days will be divided by 365.25.

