13.4 Responder Analyses

In the responder analyses, since CMAI is an interval scale that lacks a natural zero point (1 = Never), the percent change in CMAI total score will be calculated based on corrected scores after subtracting 29 points from the raw scores. For example, if a subject's Baseline CMAI total score is 79 and Week 12 CMAI total score is 29 (absent of all agitation behaviors), the percent change from Baseline to Week 12 in CMAI total score will be calculated as $[(29 - 29) - (79 - 29)] \div (79 - 29) \times 100\% = -100\%$.

Multiple types of responders will be summarized within each treatment group at each post-Baseline visit:

- $\geq 20\%$, $\geq 30\%$, $\geq 50\%$, $\geq 75\%$ and 100% reduction in the CMAI total score from Baseline
- $\geq 20\%$, $\geq 30\%$, $\geq 50\%$, $\geq 75\%$ and 100% reduction in NPI-C combined agitation and aggression domain scores from Baseline
- $\geq 20\%$, $\geq 30\%$, $\geq 50\%$, $\geq 75\%$ and 100% reduction in the individual agitation and aggression NPI-C domain scores from Baseline
- mADCS-CGIC score of 1 (marked improvement) or 2 (moderate improvement)

Other responder criteria based on point changes may be included based on examination of cumulative distribution functions and anchoring to the ADCS-CGIC.

For each of these responder analyses, the proportion of responders will be summarized by treatment group at each timepoint using observed cases and also with missing values imputed as non-response. The adjusted difference in percent responders between the treatment groups (pimavanserin group minus placebo group) using the weighting scheme of Cochran-Mantel-Haenszel and Newcombe's 95% CI stratified by geographic region will be presented. In addition, percent responders by treatment group at Week 12 will also be presented in bar charts.

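### With about 37 subjects per arm, the odds ratio planned for deaths may not exist or may mislead after a single death; SAP 14.1 has no zero-event rule and no risk difference

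*SAP*

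**What the plan says.** SAP 14.1 (Adverse Events) first tabulates event counts and the number and percentage of subjects per treatment group, including treatment-emergent serious events and fatal events. It also provides separate listings of subjects with SAEs and of subjects who died. For SAEs and death it then adds that "odds ratios and their 95% confidence intervals will be calculated using an exact logistic regression model with a single fixed effect for treatment group". There are three contrasts: "Both active arms combined versus placebo", 20 mg against placebo, and 34 mg against placebo.

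Section 14.1 does not say which point estimate is reported when the maximum-likelihood estimate is infinite. It does not say what is printed when a contrast has no events, and it plans no difference in risk.

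A difference in proportions appears only in SAP 13.4, for responders. There it is Cochran-Mantel-Haenszel weighted, with Newcombe's "95% CI stratified by geographic region will be presented".

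Protocol 7.11 has the safety monitoring committee review "formal comparisons of the rates of SAEs including deaths between the treatment groups", with the methods left to its charter.

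**The concern.** SAP 3.5 records that "enrollment (randomization) of new subjects into the study was stopped after 111 subjects were randomized", against a plan of about 432. Deaths over 12 weeks in about 37 subjects per arm may well number none or one. An exact conditional odds ratio is weakest at those counts. With no events there is nothing to estimate. With all events in one group, the maximum-likelihood estimate lies on the boundary, and the value sometimes substituted for it can look neutral or favourable to drug when the only death was on drug.

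This matters because the plan gives up any definitive reading of efficacy, so the safety comparison carries much of what the trial can contribute. The study rationale (Protocol 1.3) also names mortality among the risks that a new treatment should not increase. A blank cell gives the reader no bound on an excess of deaths, and an odds ratio of 0.50 beside 1/74 and 0/37 invites misreading.

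**Working it through.** The documents state no odds ratio, event rate or power for SAEs or deaths, so there is no figure of the plan's own to reproduce.

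**Inputs**
- 111 randomized (SAP 3.5). Allocation: "Subjects will be randomized in a 1:1:1 ratio to 1 of 3 treatment groups" (SAP 3.3). Hence 111/3 = 37 per arm and 74 on drug in the pooled contrast.
- The Safety Analysis Set is the "subset of subjects in the Randomized Analysis Set who received at least one dose of study drug" (SAP 4). The number dosed is not given. I assume exact balance and that all were dosed.
- Two-sided 95% intervals (SAP 5.1: "all confidence intervals will be 2-sided 95% confidence intervals"), so a tail of 0.025 on each side.
- Death risk: not in the documents. Assumed 0.5%, 1% or 2%, equal in all arms.

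**The model.** With one binary factor, exact logistic regression conditions on the total number of events m: P(T = t | m, ψ) ∝ C(n₁, t) · C(n₀, m − t) · ψᵗ, where T is the number of events on drug.

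**No events.** If m = 0, T can only be 0, so neither an estimate nor an interval exists. The probability is (1 − p)⁷⁴ for one dose against placebo and (1 − p)¹¹¹ for the pooled contrast.

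| Assumed death risk | No deaths, one dose vs placebo | No deaths, pooled vs placebo | Exactly one death in the trial, on drug: 74p(1 − p)¹¹⁰ |
|---|---|---|---|
| 0.5% | 69% | 57% | 21% |
| 1% | 48% | 33% | 24% |
| 2% | 22% | 11% | 16% |

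At least one of the two arms in a single-dose contrast has no deaths with probability 1 − [1 − (1 − p)³⁷]² = 97%, 90% or 72%.

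**One death, on drug.** For 1/74 against 0/37, P(T = 1) = 74ψ/(74ψ + 37), which rises towards 1 as ψ grows, so the conditional maximum-likelihood estimate is infinite. The median-unbiased value sets this probability to 0.5: 74ψ = 37, ψ = 0.50. The lower limit sets it to 0.025: ψ = 0.5 × 0.025/0.975 = 0.013. The upper limit is infinite.

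| Drug | Placebo | Median-unbiased or boundary value | Exact 95% limits |
|---|---|---|---|
| 1/74 | 0/37 | 0.50 | 0.013, infinity |
| 0/74 | 1/37 | 0.50 | 0, 19.5 |
| 1/37 | 0/37 | 1.00 | 0.026, infinity |
| 2/74 | 0/37 | 1.22 | 0.094, infinity |
| 3/74 | 0/37 | 1.96 | 0.21, infinity |

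The first two rows share a point estimate although the death is in opposite groups; only the limits tell them apart. From two events on drug the value exceeds 1. With arm sizes of 76/35 or 70/41 the first row becomes 0.46 or 0.59.

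**Risk difference.** The Newcombe interval combines Wilson limits (l, u) for each group: d − √[(p₁ − l₁)² + (u₀ − p₀)²] to d + √[(u₁ − p₁)² + (p₀ − l₀)²]. For 1/74, p = 1.35%, l = 0.24%, u = 7.27%. For 0/37, l = 0 and u = 9.41%. In percentage points:
- lower: 1.35 − √(1.11² + 9.41²) = −8.1
- upper: 1.35 + √(5.91² + 0²) = +7.3

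Unstratified results in points: 1/74 against 0/37, +1.4 (−8.1, 7.3); 1/37 against 0/37, +2.7 (−7.0, 13.8); 0/74 against 0/37, 0 (−9.4, 4.9); 0/37 against 0/37, 0 (−9.4, 9.4).

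**The case against.** The strongest reply is that the plan would not hide a death. The per-arm counts and percentages come first, the odds ratios are additional, and the deaths are listed separately. A reader would see 1/74 and 0/37 beside any odds ratio, with an interval running to infinity that nobody should take as evidence of protection. This stands: a reader might infer that deaths are reported only through odds ratios, and SAP 14.1 does not support that. What remains is that the only comparative figure would be absent, or at odds with the counts next to it.

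Second, the 0.50 depends on an estimator that the SAP does not name. The conditional maximum-likelihood estimate would be infinite, which is the right direction. Table specifications sit in a separate document (SAP 1) and may contain a rule. So the documents do not show that 0.50 would be printed, only that nothing in the SAP prevents it.

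Third, the reversal needs exactly one event in the pooled contrast, on drug. No SAE rate is given, SAEs are a broader class than deaths, and nothing here shows that the method fails for them.

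Fourth, it is tempting to suppress the odds ratio whenever one group has no events. That would discard real information: 6/37 against 0/37 has an exact lower limit of 1.28, and 9/74 against 0/37 has 1.05.

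Fifth, the Newcombe interval is not free of asymmetry. For 1/74 against 0/37 its midpoint lies slightly below zero because placebo is half the size of the pooled group. The point estimate still has the right sign, and the interval bounds the excess on both sides.

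The safety committee has its own comparisons under a charter that is not among these documents. These may serve oversight during the trial, but they do not settle what SAP 14.1 reports at the end.

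**Conclusion.** The point holds, mainly for deaths. As written, SAP 14.1 can leave the death comparison with no estimate: 22% to 69% for a single-dose contrast and 11% to 57% for the pooled one, at assumed death risks of 2% down to 0.5%. If software reports the median-unbiased value, a lone death on drug reads as 0.50 pooled or 1.00 for a single dose. The chance of exactly one death in the trial, on drug, is 16% to 24% over the same range.

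These figures assume 37 dosed subjects per arm and equal risk across arms; the death risk is an assumption, not a document figure. It does not follow that the plan conceals deaths, that the wrong-way value is certain, or that the SAE comparison is unsound. Nor does it follow that the exact odds ratio should be dropped, since its limits remain valid and can be informative when placebo has no events.

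**What to change.** In SAP 14.1:

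1. Add, for SAEs and deaths, the risk difference for 20 mg, 34 mg and both doses pooled, each minus placebo, with an unstratified Newcombe 95% interval. Say that it is unstratified: SAP 13.4 uses the region-stratified form, and the intervals shown here were not computed that way.
2. Keep the exact odds ratio wherever the contrast has at least one event.
3. When one group has no events, report the point estimate as infinite (or zero) or as not estimable, with its exact one-sided limit and the tail probability used. Do not report the median-unbiased value.
4. When neither group has an event, print not estimable for the odds ratio and let the risk difference and its interval carry the comparison.

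The cost is a few sentences in the SAP, a column in the table and a short unstratified interval calculation. The small downside is that two scales appear side by side.
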